**C. Dose Reduction Guidelines for IMP-Related Dermatologic AEs**

Dose delay and/or inpatient dose-reduction(s) will be required upon occurrence of Grade 3 anti-EGFR-associated dermatologic AE, and should be implemented according to the following tables (**Table 24**, **Table 25**):

Table 24: Dose Reduction for Grade 3 Dermatologic AEs - Sym004			
Dermatologic AE Grade 3	Immediate Action	Outcome Improvement	Sym004
First occurrence	Delay dose	Grade ≤1	Continue at same dose
		Grade 2	Reduce to 4.5 mg/kg
		No improvement	Discontinue
Second occurrence	Delay dose	Grade ≤1	Continue at same dose
		Grade 2	At dose of 6.0 mg/kg: Reduce to 4.5 mg/kg At dose of 4.5 mg/kg: Reduce to 3.0 mg
		No improvement	Discontinue
Third occurrence	Delay dose	Grade ≤1	Continue at same dose
		Grade 2	At dose of 6.0 mg/kg: Reduce to 4.5 mg/kg At dose of 4.5 mg/kg: Reduce to 3.0 mg/kg At dose of 3.0 mg/kg: Discontinue
		No improvement	Discontinue
Fourth occurrence	Discontinue	Any	Discontinue

Abbreviations (in alphabetical order): kg, kilogram; mg, milligram

Note: Dose reductions for 9 mg/kg loading NA. For dose delays, re-assess after ≤ 2 weeks. Longer delays are allowed if no recovery to < Grade 2 after 2 weeks

Table 25: Dose Reduction for Grade 3 Dermatologic AEs - Futuximab or Modotuximab			
Dermatologic AE Grade 3	Immediate Action	Outcome Improvement	Futuximab or Modotuximab
First occurrence	Delay dose	Grade ≤1	Continue at same dose
		Grade 2	Reduce to 1.5 mg/kg
		No improvement	Discontinue
Second occurrence	Delay dose	Grade ≤1	Continue at same dose
		Grade 2	At dose of 3.0 mg/kg: Reduce to 1.5 mg/kg At dose of 1.5 mg/kg: Discontinue
		No improvement	Discontinue

Abbreviations (in alphabetical order): kg, kilogram; mg, milligram

Note: Dose reductions for 9 mg/kg loading NA. For dose delays, re-assess after ≤ 2 weeks. Longer delays are allowed if no recovery to < Grade 2 after 2 weeks

In each case, the next treatment should be delayed, and the patient’s condition should be re-assessed after 1-2 weeks. Treatment should be delayed further if the AE remains at Grade 3 after 2 weeks.

In the case of a Grade 2 dermatologic AE which is locally debilitating for the patient, the guidelines outlined above may be followed at the Investigator’s discretion.

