
AE Management
	
Dose Delay AEs that do not meet the protocol discontinuation criteria, but nevertheless warrant dose modification, may be managed by temporary dose delay to allow for amelioration of the toxicity.
 
Dose Reduction In the event of Grade 3 treatment-related AEs that are self-limiting or can be managed by supportive care or other therapy, the patient may continue in the study if there is evidence of response, disease stabilization, or other clinical benefit, but must do so at a reduced dose of IMP. Patients may not be retreated until retreatment criteria are met. Once a patient has undergone dose reduction for any reason, the patient will continue to be treated at the reduced dose throughout the remainder of their time on study treatment.

Infusion-Related Reactions
	
Instructions for the grading and management of IRRs are provided. In all cases the Investigator should use best clinical judgment in managing such reactions.
 
 
• For Grade 3 reactions, the infusion will be STOPPED. The patient will be either discontinued from treatment or must receive subsequent treatments at a reduced dose and at a prolonged infusion rate.
 
• For Grade 4 reactions, the infusion will be STOPPED and the patient will be permanently discontinued from treatment.
 

Dermatologic Toxicity
	
Patients will be monitored weekly for evidence of dermatologic AEs.
 
Dose delay and/or inpatient dose-reduction(s) will be required upon occurrence of Grade 3 AEs, and may be implemented in the event of a Grade 2 dermatologic reaction that is debilitating for the patient.
 
Recommendations for management of Grade 1 to 3 dermatologic AEs are provided. Patients must be withdrawn from IMP treatment in the event of a Grade 4 dermatologic AE.

Hypomagnesemia, Hypocalcemia, and Hypokalemia
	
Patients will be monitored weekly for hypomagnesemia, hypocalcemia, and hypokalemia. In the event of Grade 3-4 hypomagnesemia, repletion is required as well as predosing electrocardiograms (ECGs) to monitor for QTc prolongation. For Grade 4 hypomagnesemia that is refractory to IV magnesium-replacement therapy, dosing with Sym004 should be delayed or reduced. Full management instructions are provided in the protocol.

SAFETY MONITORING
	

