#### 8.2.1.1 Instructions for Infusion Prolongation

For IRRs, the following infusion prolongation instructions are provided (for premedication instructions, see [Section 8.1.1](#)).

- For Grade 1 reactions, the infusion may be slowed to 50% of the prior rate such that the remaining dose to be delivered is administered 2× longer than the amount of time that was initially scheduled.
- For Grade 2 reactions, the infusion should be interrupted for a minimum of 30 minutes, and at least until there is either amelioration to ≤ Grade 1 severity or return to baseline status. Supportive care should be provided. The infusion should then be restarted at 50% of the prior rate, as described above. Subsequent infusions should be administered at the prolonged rate.
- For Grade 3 reactions, the infusion will be STOPPED and supportive care will be provided. The patient will be either discontinued from treatment, or must receive subsequent treatments at a reduced dose and at a prolonged infusion rate (slowed to 50% of the prior rate or longer).
- For Grade 4 reactions, the infusion will be STOPPED and supportive care will be provided. The patient will be permanently discontinued from treatment.

In all cases, the Investigator should use best clinical judgment in managing such reactions.

All infusion interruptions and subsequent prolongations, including modified infusion times, as well as the toxicity that necessitated them, will be clearly documented on the appropriate page of the patient's CRF.

Note: Any assessments to be performed or samples to be collected (e.g., vital signs, PK) at the end of or following the EOI will still be performed or collected beginning at the delayed EOI timepoint

Guidelines for the grading and management of IRRs of all severities are provided ([Appendix 6](#)).

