## **8.2.3 Dose Reduction**

*All reductions of IMP dose must be documented on the appropriate page of the patient's CRF. Dose reduction may occur either during treatment cycles, or between cycles, as clinically indicated.*

In the event of Grade 3 treatment-related AEs that are self-limiting or manageable by supportive care or other therapy, the patient may continue in the study if there is evidence of OR, SD, or other clinical benefit, but must do so at a reduced dose of IMP. Patients may not be retreated until retreatment criteria are met (see [Section 6.7.1](#)).

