### B. Management of Hypomagnesemia

Patients receiving IMP will be monitored weekly for evidence of hypomagnesemia, which should be managed as follows (Table 27):

Table 27: Management of Hypomagnesemia and QTc Prolongation	
Grade	Action
Grade 1-2	No replacement therapy required, weekly monitoring to continue, but may be administered at treating physician's discretion, weekly monitoring to continue
Grade 2 or higher	Use of concomitant QTc-prolonging drugs* should be discontinued unless urgently needed for medical care and no alternative therapy is available
Grade 3-4	Administer MgSO 4 (6 to 10g IV) at minimum 2 times per week until ≤ Grade 1 Perform predosing ECG (required) to monitor for QTc prolongation**  In the event of Grade 3 QTc prolongation potentially due to hypomagnesemia, Sym004 administration should be delayed while magnesium repletion is undertaken  Sym004 may be restarted with continued intensive magnesium therapy at the same dose or at a reduced dose once hypomagnesemia returns to ≤ Grade 1 severity, and once the QTc returns to WNL or baseline status  In the event of Torsade de pointes (TdP) or other life-threatening arrhythmias discontinue Sym004
Grade 4	For Grade 4 hypomagnesemia that is refractory to IV magnesium-replacement therapy, dosing with IMP should be delayed or reduced .

Abbreviations (in alphabetical order): g, gram; IV, intravenous

\* Listings of QTc prolonging drugs may be found at: <<https://crediblemeds.org/index.php?cID=222>>

\*\* ECG is required before IMP administration to monitor QT prolongation that may result in severe arrhythmias such as TdP.

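### Table 24 sets the Sym004 dose after a Grade 3 skin event by counting events, so its first two rows misfire for a patient already reduced for an uncounted reason

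*Protocol*

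**What the plan says.** Part C of Appendix 7 (Protocol) governs Grade 3 skin events. It says that dose delay or reduction "should be implemented according to the following tables". Table 24 (Sym004) has one row per occurrence of a Grade 3 dermatologic event. For the outcome of improvement to Grade 2 only:

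- First occurrence: "Reduce to 4.5 mg/kg", with no reference to the current dose.
- Second occurrence: an entry for 6.0 mg/kg, then "At dose of 4.5 mg/kg: Reduce to 3.0 mg". No 3.0 mg/kg entry follows.
- Third occurrence: entries for 6.0 and 4.5 mg/kg, then "At dose of 3.0 mg/kg: Discontinue".

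Other sections reduce Sym004 for reasons that this count does not include:

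- Section 8.2.1.1, Grade 3 infusion reaction: the patient stops, or "must receive subsequent treatments at a reduced dose and at a prolonged infusion rate".
- Section 8.2.3, any manageable Grade 3 related event: the patient may continue, "but must do so at a reduced dose of IMP".
- Table 27, hypomagnesemia with QTc prolongation: "Sym004 may be restarted with continued intensive magnesium therapy at the same dose or at a reduced dose".
- Synopsis (repeated for IMP in Table 27): "For Grade 4 hypomagnesemia that is refractory to IV magnesium-replacement therapy, dosing with Sym004 should be delayed or reduced".
- Appendix 7 C: the investigator may apply the same guidelines to a Grade 2 skin event that is locally debilitating.
- Table 23: reduction may be discussed with the Sponsor for fissures that persist. The trigger is a treatment step, not a grade.

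The general rules are Table 6 (6 to 4.5 to 3 mg/kg, at most two reductions), Section 9.1 (discontinue an Arm A patient who needs more than two), and Sections 6.5.4.1 and 8.2.4 (no re-escalation).

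**The concern.** Event number stands in for current dose in rows 1 and 2. That works only if every earlier reduction followed a counted Grade 3 skin event, and the protocol does not make that so. Section 2.6 names dermatologic toxicities and hypomagnesemia as the most frequent events of Grade 3 or higher on this regimen, so one patient could plausibly have both.

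At stake is the dose given after a Grade 3 skin event that has improved only partly. Amendment 5 ends the efficacy objectives, but it leaves doses unchanged, lets the two enrolled patients stay on Sym004 until progression, and does not withdraw Appendix 7. Dosing safety is the part of the protocol still in use.

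**Working it through.** There is no published figure to reproduce. The check compares Table 24 with the general rules for each occurrence and current dose, for the recovery-to-Grade-2 outcome.

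Inputs: Table 24 as printed; Table 6 for the steps 6.0 to 4.5 and 4.5 to 3.0 mg/kg; Section 9.1 for discontinuation when a further reduction is needed at 3.0 mg/kg.

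| Occurrence | Current dose (mg/kg) | Table 24 | Table 6 with 9.1 | Agree? |
|---|---|---|---|---|
| 1 | 6.0 | 4.5 | 4.5 | yes |
| 1 | 4.5 | 4.5 (no change) | 3.0 | no |
| 1 | 3.0 | 4.5 (not a reduction) | discontinue | no |
| 2 | 6.0 | 4.5 | 4.5 | yes |
| 2 | 4.5 | 3.0 | 3.0 | yes |
| 2 | 3.0 | no entry | discontinue | no |
| 3 | 6.0 | 4.5 | 4.5 | yes |
| 3 | 4.5 | 3.0 | 3.0 | yes |
| 3 | 3.0 | discontinue | discontinue | yes |

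Six of nine agree. At 4.5 mg/kg, row 1 gives 4.5/4.5 − 1 = 0%, where the Table 6 step is 3.0/4.5 − 1 = −33%.

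Which combinations can occur?

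- If the only reductions are those that Table 24 makes for counted Grade 3 events, the possible doses are {6.0} at the first event, {6.0, 4.5} at the second and {6.0, 4.5, 3.0} at the third. That is 1 + 2 + 3 = 6 combinations, exactly the six that agree.
- If uncounted reductions are allowed, all three doses are possible at every event, so all nine combinations can occur. Row 1 at 4.5 needs one uncounted reduction, row 1 at 3.0 needs two, and row 2 at 3.0 needs at least one.

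This takes the table's own column heading at its word: a Grade 2 skin event handled under the same guidelines is not a Grade 3 occurrence.

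The other outcomes do not depend on dose: recovery to Grade 1 or below means the same dose, and no improvement means discontinue.

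With rows 1 and 2 written like row 3, all nine combinations agree.

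**The case against.** The strongest reply is that the protocol as a whole already gives the answer. Table 6 takes 4.5 to 3 mg/kg, its note on the two-reduction limit refers to Appendix 7, Section 9.1 discontinues a patient who needs a third reduction, and two sections bar any increase. The Medical Monitor is also available for consultation on delays and restarts (Section 12.2). This largely stands. The defect is an inconsistency between Table 24 and the general rules, not a lack of guidance. What remains is that sites are told to follow the table, Section 13.4.1 allows no departures from the plan, and nothing says which section prevails. Nor can a site assume that the general rules override the table. For skin events Table 24 already departs from Section 8.2.3, by allowing the same dose after recovery to Grade 1 or below, and from Section 8.2.2.2, by allowing a restart at Grade 2. Section 6.7.1 accepts a controlled Grade 2 rash for retreatment.

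A second reply is that row 1 at 4.5 mg/kg does not contradict Appendix 7 itself, whose lead-in asks for delay and/or reduction, and every row delays first. That is fair, and it makes this the weakest of the three mismatches. The conflict there is with Section 8.2.3 and Table 6.

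A reader might infer that the protocol orders a dose increase at 3.0 mg/kg. It does not. The cell is worded as a reduction, and Sections 6.5.4.1 and 8.2.4 forbid an increase. The sound statement is that the cell cannot be applied at that dose. A reader might also infer that only non-skin reductions cause the problem. The provisions for debilitating Grade 2 skin events and for fissures show otherwise.

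**Conclusion.** The inconsistency is real and minor. Three of nine event-by-dose combinations conflict with Table 6 and Section 9.1 or have no entry, all in the recovery-to-Grade-2 outcome and all requiring an earlier reduction outside the Grade 3 skin count. At most the two patients on Sym004 are exposed, and nothing in the protocol says that either has had a dose reduction. The output is patient profiles or listings, so no statistical result changes.

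The protocol gives no rate for the sequence needed: an uncounted reduction, then a Grade 3 skin event, then recovery only to Grade 2. A reader might take the 20.2% of Sym004-05 patients on the 9/6 regimen with an event leading to dose reduction (Section 2.4.1) as a guide. It covers all causes, skin included, and says little about this sequence, so no probability is offered here.

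**What to change.** In Table 24, make the Grade 2 outcome in rows 1 and 2 depend on the current dose, as row 3 does: at 6.0 reduce to 4.5 mg/kg; at 4.5 reduce to 3.0 mg/kg; at 3.0 discontinue. In the same edit, complete the unit in row 2, where 3.0 mg should read 3.0 mg/kg.

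For consistency, align Table 25 row 1 with its row 2: at 3.0 reduce to 1.5 mg/kg; at 1.5 discontinue. No current patient is affected by Table 25, since both are on Sym004.

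The cost is a few table cells in the next amendment under Section 13.4.1, with the usual IRB/EC approval at the one active site. No procedure or data collection is added.

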#### 5.1.1 Formulations

Sym004, futuximab, and modotuximab are each clear to opalescent, colorless to slightly yellow, liquid formulations for IV infusion. Vialled supplies will be provided by the Sponsor with the following volume, concentration, and total content:

- Sym004
  - Nominal fill volume of 20 mL
  - At a concentration of 25 mg/mL for a total vial content of 500 mg
- Futuximab
  - Nominal fill volume of 10 mL
  - At a concentration of 25 mg/mL for a total vial content of 250 mg
- Modotuximab
  - Nominal fill volume of 10 mL
  - At a concentration of 25 mg/mL for a total vial content of 250 mg

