### 5.7 Dose Calculation

The dose to be administered will be multiplied by the patient's weight in kilograms to arrive at the total dose to be delivered. In situations where this calculation results in a value with an unwieldy number of decimal places, it is permissible to round the value to the nearest "tenth". As a convention, values > 5 should be "rounded" to the next higher number.

Dose adjustments should be made in the event of noted weight change ( $\pm 10\%$ ; less at the site's discretion or if required by institutional procedures) as measured at the beginning of each dosing cycle (CxD1). Adjustments may be made in the event of lesser incremental changes in weight and/or more frequently at the site's discretion.

Dosing information will be recorded on the appropriate Accountability Form in use. This inventory will be maintained throughout the duration of the trial and will be periodically reviewed by a representative of the Sponsor.

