#### 6.5.4.1 Dose

Doses of IMP to be administered are as follows:

- Arm A
  - Loading dose: 9 mg/kg on C1D1
  - Maintenance doses: 6 mg/kg weekly ( $\pm$  2 days), beginning on C1D8
- Arm B and Arm C
  - Loading dose: 4.5 mg/kg on C1D1
  - Maintenance doses: 3 mg/kg weekly ( $\pm$  2 days), beginning on C1D8

Changes in Dose to be Administered: Patients will continue to be treated with IMP at that same dose unless dose reduction is necessary due to the occurrence of an AE(s) warranting such action. Once the dose of any IMP is reduced, there will be no dose reescalation. There will be no inpatient dose-escalation.

Dose adjustments should be made in the event of noted weight change ( $\pm$  10%; less at the site's discretion or if required by institutional procedures) as measured at the beginning of each dosing cycle (CxD1). Adjustments may be made in the event of lesser incremental changes in weight and/or more frequently at the site's discretion.

Crossover Dose of Sym004: At the EOC2, ongoing patients from Arm B and Arm C will be crossed-over from futuximab or modotuximab to Sym004; crossover may occur prior to the EOC2 in the event of early radiographic documentation of PD.

Upon crossover, Sym004 will be administered at the dose level that contains the corresponding dose level of the individual antibody futuximab or modotuximab as was previously being administered (prior to crossover). Therefore, patients receiving futuximab or modotuximab at the dose of 3 mg/kg or the reduced dose of 1.5 mg/kg will crossover to receive Sym004 at the dose of 6 or 3 mg/kg, respectively.

Sym004 treatment may be initiated at least one week after the latest dose of futuximab or modotuximab, unless AEs prevent this according to the protocol retreatment criteria (**Section 6.7**). Dosing of Sym004 may continue until further PD is observed.

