#### 6.7.1 Retreatment Guidelines

Prior to starting any new cycle, a patient must meet the following criteria:

- ANC  $\geq$  1,000 per mm^3
- Platelets  $\geq$  75,000 per mm^3

- Any ongoing IMP-related AE should NOT meet study discontinuation criteria
- Any ongoing IMP-related AE should have either ameliorated to  $\leq$  Grade 1 severity, returned to baseline status, or resolved, with the exceptions of:
  - Grade 2 alopecia,
  - Grade 2 clinical events that are being adequately controlled with BSC (e.g., nausea, vomiting, diarrhea, fatigue, rash), and
  - Asymptomatic laboratory abnormalities that are considered clinically insignificant, clinically uncomplicated, and/or that are resolving spontaneously or with conventional medical interventions (Grade 2 hypomagnesemia not included as an exception; [Appendix 8](#))

Should the above criteria not be met, dosing must be delayed until further evaluation is completed and it is determined that the patient is eligible for continued treatment (for information on dose delays, see [Section 8.2.2](#)). If a delay is required to allow for amelioration of ongoing AEs, additional cycles should be initiated within approximately 2 weeks after the completion of the previous cycle, if feasible.

### 6.7.2 Cycle 2

Administration will be at the same dose (unless dose reduction is necessary) and infusion duration established for the patient during the previous cycle, and on the same weekly schedule provided retreatment guidelines are met.

### 6.7.3 Treatment after Cycle 2

**As of Amendment 5:** Due to the Sponsor's decision to discontinue the trial (effective 20Dec2018), the frequency of disease status evaluations will be per either institutional guidelines or Investigator discretion. Enrolled patients (2 total) have been either crossed over to receive or are receiving Sym004, and may continue to receive Sym004 until confirmation of PD. The pre-Amendment 5 plan for continued treatment after Cycle 2 as detailed below will not be followed.

Disease assessment and tumor measurements will be conducted at the EOC2. Instructions for continued dosing are as follows:

- Patients assigned to Arm A (Sym004) with a documented OR or SD will continue to receive Sym004; patients with documented PD at the EOC2 will be discontinued from study.

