### **8.2.3.1 Dose Reduction Schedule**

If toxicity is to be managed by dose reduction, the IMP dose will be decreased as follows ([Table 6](#), [Table 7](#)):

Table 6: Dose-Reduction of Sym004		
Sym004 Dose	First Reduction	Second Reduction
6 mg/kg	4.5 mg/kg	3 mg/kg

Abbreviations (in alphabetical order): kg, kilogram; mg, milligram

Note: Dose Reductions for 9 mg/kg loading dose NA; the number of dose reductions allowed is limited to 2 ([Appendix 7](#))

Table 7: Dose-Reduction of Futuximab and Modotuximab		
Futuximab or Modotuximab Dose	First Reduction	Second Reduction
3 mg/kg	1.5 mg/kg	Not applicable

Abbreviations (in alphabetical order): kg, kilogram; mg, milligram;

Note: Dose Reductions for 4.5 mg/kg loading dose NA; the number of dose reductions allowed is limited to 1

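### Table 24 gives one reduced Sym004 dose as a flat 3.0 mg where 3.0 mg/kg is meant

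*Protocol*

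**What the plan says.** Appendix 7, part C makes dose delay and/or reduction compulsory after a Grade 3 anti-EGFR skin event, and says this "should be implemented according to the following tables". Table 24 is the one for Sym004. It is organised by occurrence of the event (first to fourth) and by how far the event improves during the delay.

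For a second occurrence that improves to Grade 2, the line for a patient at the first reduced level reads "At dose of 4.5 mg/kg: Reduce to 3.0 mg". For a third occurrence with the same improvement, the corresponding lines read "At dose of 4.5 mg/kg: Reduce to 3.0 mg/kg At dose of 3.0 mg/kg: Discontinue".

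Two other places fix the same dose level or the way it is calculated:

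- Section 8.2.3.1 opens "If toxicity is to be managed by dose reduction, the IMP dose will be decreased as follows" and leads to Table 6, whose Sym004 ladder is 6 mg/kg, then 4.5 mg/kg, then 3 mg/kg.
- Section 5.7 multiplies the dose level by the patient's "weight in kilograms to arrive at the total dose to be delivered".

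**The concern.** A bare 3.0 mg is a different instruction from 3.0 mg/kg, and nothing in the Protocol supports a flat dose of any of the three products. The cell is in a table that sites are told to apply, in the current body of the document and not in the amendment history. Section 13.4.1 allows neither departures from the experimental plan nor waivers, so a site should be given the right instruction and not have to infer it.

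The table also remains live. Section 6.5.4 states that Amendment 5 leaves the doses unchanged. Section 6.7.3 says the two enrolled patients "have been either crossed over to receive or are receiving Sym004, and may continue to receive Sym004 until confirmation of PD". Appendix 7 is not marked as withdrawn. Section 2.6 names skin toxicity, with hypomagnesemia, as the most frequent event of Grade 3 or above on this regimen, so the table deals with an expected problem.

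The route to the cell is direct. A first Grade 3 skin event that improves to Grade 2 takes the patient from 6 to 4.5 mg/kg. A second that does the same lands on this line, which is the first place in Table 24 where the second reduction is stated.

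**Working it through.** **Which value is intended.** The sources side by side:

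| Source | Step | Dose given |
|---|---|---|
| Table 24, second occurrence, improved to Grade 2 | from 4.5 mg/kg | 3.0 mg |
| Table 24, third occurrence, improved to Grade 2 | from 4.5 mg/kg | 3.0 mg/kg |
| Table 6, second reduction | from 4.5 mg/kg | 3 mg/kg |

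The first row is the only one without the per-kilogram unit. Elsewhere in Tables 24 and 25 the doses carry it, including the line just above in the same cell (6.0 to 4.5 mg/kg). The intended value is therefore 3.0 mg/kg.

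**Size of the slip if read literally.**

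Inputs:

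- Printed dose: 3.0 mg (Table 24).
- Intended dose level: 3.0 mg/kg (Table 6; Table 24, third occurrence).
- Vial strength, Section 5.1.1: "At a concentration of 25 mg/mL for a total vial content of 500 mg".
- Body weight: the Protocol gives none, so 60 to 90 kg is assumed.

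Intended dose = dose level × weight; volume drawn = dose ÷ 25 mg/mL.

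- Printed: 3.0 mg ÷ 25 mg/mL = 0.12 mL.
- Intended at 60 kg: 3.0 × 60 = 180 mg; 180 ÷ 25 = 7.2 mL.
- Intended at 90 kg: 3.0 × 90 = 270 mg; 270 ÷ 25 = 10.8 mL.
- Ratio of intended to printed: 180 ÷ 3.0 = 60 at 60 kg, and 270 ÷ 3.0 = 90 at 90 kg.
- Printed dose per kilogram: 3.0 ÷ 60 = 0.05 mg/kg, and 3.0 ÷ 90 = 0.033 mg/kg.

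For scale, Section 2.4.2 gives 0.4 mg/kg as the lowest weekly level in the Phase 1 escalation. The literal dose is below even that.

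**How often it could matter.** At most two patients can reach the cell. The Protocol gives no rate for a second Grade 3 skin event improving only to Grade 2 in a patient already at 4.5 mg/kg, and none is assumed here.

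**The case against.** Several points can be made on the other side.

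- **The unit may have been lost when the PDF was read.** It is missing at the end of a multi-line cell. This cannot be ruled out without the source page, but the neighbouring cells kept their units, so a slip in the document is the likelier explanation. One look at the source settles it.
- **The document corrects itself.** Table 6 and the third-occurrence row leave no rival reading, and the line itself starts from a dose in mg/kg. This is true, and it is why the likely result is a query at restart and not a wrong infusion. It does not make the printed instruction right.
- **The cell is rarely reached.** Accrual is closed and two patients remain. Section 8.2.2.2 also appears to allow restart after a delay only at Grade 1 or below, at baseline status, or on resolution, which would leave little room for a Grade 2 row. However, Section 6.7.1 excepts Grade 2 events under adequate control, rash among them, so the row can still be reached.
- **The crossover rule is weak support.** Section 6.5.4.1 says patients on the reduced single-antibody dose "will crossover to receive Sym004 at the dose of 6 or 3 mg/kg, respectively", but Amendment 5 has ended that crossover plan. This is fair: it shows only that 3 mg/kg was a recognised Sym004 level. Table 6 and the third-occurrence row carry the point without it.

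These arguments limit the importance of the error. None shows that a flat 3.0 mg is correct.

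**Conclusion.** The point holds as a minor correction. One cell of an operative dosing table states a dose that contradicts the Protocol's own reduction ladder and the same step elsewhere in the same table. Followed to the letter it would give a 60- to 90-fold underdose, on the assumed weight range of 60 to 90 kg. The realistic cost is much smaller: a pharmacy query at a restart, for at most two patients. It has no bearing on the design, the data or any analysis. The conclusion that the unit is missing does not depend on the assumed weights, which serve only to show the size. It does rest on the text as supplied matching the source page.

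**What to change.** In Appendix 7, Table 24, second occurrence, Grade 2 row, give the reduced dose as 3.0 mg/kg, after checking the source page.

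As tidying only, the note under Table 25 refers to a 9 mg/kg loading dose for futuximab and modotuximab. Their loading dose is 4.5 mg/kg (Section 6.5.4.1 and the note under Table 7), so that figure can be corrected at the same time. It changes no dose.

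The cost is one unit added in one cell, plus one figure in a note, with no effect on design, data or analysis.
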